### **2.2.2 Vectibix® (Panitumumab) Clinical Experience in mCRC – Efficacy**

Results from a multicenter, randomized (1:1), controlled phase 3 study (Study 20020408) of panitumumab plus best supportive care (BSC) vs. BSC alone demonstrated a statistically significant improvement in the primary efficacy endpoint of progression-free survival in subjects with metastatic colorectal cancer (mCRC) who had disease progression during or after prior standard fluoropyrimidine, irinotecan, and oxaliplatin chemotherapy, ie, a 46% reduction in the rate of disease progression or death compared with BSC alone. Furthermore, 10% of subjects in the panitumumab plus BSC group and no subject in the BSC alone group had an objective response according to modified Response Evaluation Criteria in Solid Tumours (RECIST) criteria by central review (all partial responses). An additional 26% of subjects in the panitumumab plus BSC group and 10% of subjects in the BSC alone group had a best response of stable disease.

Results from 5 supportive mCRC studies (20025405, 20030167, 20030250, 20030194, and 20050216) confirmed the anti-tumour activity of panitumumab (as measured by objective response rates) in subjects with mCRC who failed prior irinotecan and/or oxaliplatin therapy. In addition, after completion of Study 20020408, a prespecified statistical analysis plan was defined to evaluate *KRAS* status in relation to outcomes; this plan was finalized prior to any *KRAS* testing. This analysis of Study 20020408 showed that *KRAS* mutation status serves as a predictive biomarker of response in the setting of panitumumab monotherapy in subjects with mCRC who have failed prior therapy. These data suggest that improvements in progression-free survival (PFS) and objective response rate are restricted to subjects with *KRAS* wild-type tumours.

Results from 2 phase 3, pivotal studies (20050203 and 20050181) provide efficacy data on panitumumab in combination with chemotherapy as initial or second-line treatment in the mCRC setting. Both of these studies were open-label, randomized trials of panitumumab plus chemotherapy versus chemotherapy alone. Oxaliplatin-based chemotherapy (FOLFOX) and irinotecan-based chemotherapy (FOLFIRI) were selected for these studies because they were among the standard of care in this setting when these trials were designed.

---

Results from the 20050203 and 20050181 pivotal studies demonstrated that in subjects with wild-type *KRAS* tumour status, panitumumab resulted in a statistically significant and clinically relevant improvement in PFS when combined with chemotherapy relative to chemotherapy alone in Study 20050203 (FOLFOX) (median of 10.0 vs. 8.6 months; hazard ratio 0.799; 95% confidence interval (CI): 0.674, 0.946; log-rank test  $p = 0.0092$ ) and Study 20050181 (FOLFIRI) (median of 6.7 vs. 4.9 months; hazard ratio 0.820; 95% CI: 0.692, 0.972; log-rank test  $p = 0.0231$ ).

In both phase 3 studies, the primary analysis of overall survival (OS) showed a trend towards improvement with panitumumab plus chemotherapy relative to chemotherapy alone in subjects with wild-type *KRAS* tumours (absolute difference in median OS of 4.2 months and 2.0 months in Studies 20050203 (FOLFOX) and 20050181 (FOLFIRI), respectively), but did not demonstrate a statistically significant difference between treatment arms. The incidence of subsequent anti-EGFR therapy was higher in subjects receiving chemotherapy alone compared with those receiving panitumumab plus chemotherapy; these imbalances between treatment arms may have influenced the analysis of OS. In Study 20050203, PFS and OS were shorter in subjects with mutant *KRAS* tumours in the panitumumab plus FOLFOX arm compared with the FOLFOX alone arm. In Study 20050181, the addition of panitumumab to FOLFIRI had no positive or negative effect on PFS, OS, or objective response rate in subjects with mutant *KRAS* tumours. In subjects with wild-type *KRAS* tumours, panitumumab resulted in a higher objective response rate (ie, confirmed complete or partial response) when combined with chemotherapy relative to chemotherapy alone in Study 20050203 (57% vs. 48%) and Study 20050181 (36% vs. 10%). In addition, 3 phase 2 studies (20060314, 20050184, and 20060277) supported the efficacy data for the use of panitumumab in combination with either oxaliplatin- or irinotecan-based chemotherapy as initial or second-line treatment for subjects with mCRC. Results of the phase 2 studies for PFS, OS, and objective response were generally consistent with the phase 3 studies. Improvement in objective response rate and PFS were observed for subjects with wild-type *KRAS* tumours compared with those with mutant *KRAS* tumours in these phase 2 studies.

Refer to the current Vectibix® [panitumumab] SPC for further details regarding the efficacy of panitumumab as monotherapy and in combination with chemotherapy in mCRC.

---

### 2.3 Rationale

The data which will be collected is to anticipate expected reimbursement agency requirements in Germany and France. The requirements focus on gaining a clear understanding of the real life use of Vectibix® in accordance with the new label, and so the objectives in this study have been defined to meet such requirements. This study will therefore be conducted to gain understanding of Vectibix® use for the treatment of subjects with wild-type *KRAS* mCRC, in first-line in combination with FOLFOX or second-line in combination with FOLFIRI in subjects who have received first-line fluoropyrimidine-based chemotherapy (excluding irinotecan).

### 2.4 Hypotheses

The analysis of data in this study will be descriptive in nature therefore no formal hypotheses will be tested. The data will describe a realistic characterization of the mCRC patient population in routine clinical practice, treated with Vectibix® as first-line treatment in combination with FOLFOX or second-line treatment in combination with FOLFIRI in patients who have received first-line fluoropyrimidine-based chemotherapy (excluding irinotecan).

## 3. STUDY DESIGN

This is a multicenter, observational, prospective cohort study in France and Germany.

All treatment centres (inpatient and outpatient) with a focus on treating subjects with mCRC in participating countries will be prospectively defined for potential inclusion in the study. Centres will be selected to represent academic, oncology, specialist and private settings, and to provide geographical diversity within each country. A subject log will be maintained and details of all patients not enrolled will be recorded, as permitted by local regulations, including reason for non-enrolment.

Subjects with wild-type *KRAS* mCRC receiving Vectibix® treatment in combination with chemotherapy as first-line treatment in combination with FOLFOX or second-line treatment in combination with FOLFIRI in patients who have received first-line fluoropyrimidine-based chemotherapy (excluding irinotecan) will be eligible for entry to the study.

Enrolled subjects must have received at least one infusion of Vectibix® in combination with chemotherapy a maximum of 42 days before entering study. Retrospective data will be collected from Baseline (which occurs prior to the first dose of Vectibix®) up to the

---

point of enrolment. Subsequent chemotherapy cycles and Vectibix® doses will be recorded prospectively.

Each subject will have data collected until approximately 30 days after the end of Vectibix® treatment, death, withdrawal of consent, loss to follow-up, or up to 12 months from the first dose of Vectibix®, whichever occurs first.

Data will be obtained from routine clinical records and transcribed onto an electronic case report form (eCRF) which will be in three parts:

- (i) Baseline visit
- (ii) Follow-up visit – or next patient visit throughout the observation period based on physician preference for follow up.
- (iii) End of observation– approximately 30 days after the end of Vectibix® treatment or 12 months from the initiation of Vectibix®, whichever occurs first (unless preceded by subject death, loss to follow up or withdrawal of consent).

### **3.1 Number of Centres**

Approximately 50-100 centres will participate in this study in total. A large number of centres are necessary to ensure we capture sufficient patients as the change in the label for Vectibix® in Europe is relatively recent. Centres that do not enrol subjects within 3 months of centre initiation may be closed if it is likely that they will not be able to enrol a sufficient number of subjects in the required timeframe. We aim to include a wide selection of hospital types that include large specialist referral centres as well as smaller general hospitals and each country will be required to include a representative sample of different types of hospitals (academic, specialist, general hospitals, private etc). In Germany many patients may also be treated in an outpatient oncology clinic setting so we represent these centres too.

### **3.2 Number of Subjects**

Participants in this observational study shall be referred to as “subjects”. This study will enrol approximately 740 subjects (up to 350 in France and up to 390 in Germany) in total. Enrolment into the study will be capped by country according to these numbers.

### **3.3 Estimated Study Duration**

#### **3.3.1 Study Duration for Participants**

The duration of observation will vary for each subject. Subjects will be followed-up until approximately 30 days after the end of Vectibix® treatment, death, withdrawal of consent, loss to follow-up, or up to 12 months from the first dose of Vectibix®, whichever occurs first.

---

It is anticipated that subject enrolment will be ongoing for 12 months.

Including the 12-months observation period for each subject, it is anticipated the study duration will be approximately 24 months.

### **3.3.2 End of Study**

The end of the study for an individual subject is defined as the last day that protocol-specified observation data is collected for an individual subject. Subjects will be followed-up until approximately 30 days after the end of Vectibix® treatment, death, withdrawal of consent, loss to follow-up, or up to 12 months from the first dose of Vectibix®, whichever occurs first.

The end of study is defined as when the last subject is followed-up for the purposes of final collection of observation data. The study will end when the last subject remaining on the study either completes the 12-month observation period, dies, withdraws informed consent, or is lost to follow-up, whichever occurs first.

### **3.4 Subject Eligibility**

Before any study-specific data are recorded, the appropriate written informed consent must be obtained if required. The decision to prescribe treatments must have been freely undertaken by the clinician prior to consideration for the subject to be included in the study. Therefore, treatment administration will be independent and dissociated from participation in the study.

### **3.5 Inclusion Criteria**

- 3.5.1 Subject is ≥18 years of age at date of enrolment
- 3.5.2 Histologically or cytologically confirmed carcinoma of colon or rectum
- 3.5.3 Subject with metastatic carcinoma of colon or rectum
- 3.5.4 Confirmed wild-type KRAS status of tumour
- 3.5.5 Subjects whose care will be managed primarily by the enrolling physician and/or all records will be available
- 3.5.6 Tumour assessment (ie, CT/MRI) within 12 weeks (84 days) prior to first Vectibix® infusion
- 3.5.7 Subjects treated with at least one infusion of Vectibix® in combination with chemotherapy a maximum of 42 days before entering study: first-line in combination with FOLFOX or second-line in combination with FOLFIRI in subjects who have received first-line fluoropyrimidine-based chemotherapy (excluding irinotecan) for treatment of wild-type KRAS mCRC per approved prescribing information
- 3.5.8 Subject or subject's legally acceptable representative has provided informed consent (for countries where required per local regulations)

---

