## Glossary

Abbreviation or Term	Definition/Explanation
5-FU	5-fluorouracil
ADR	Adverse drug reaction
BSC	Best supportive care
CI	Confidence interval
CRC	Colorectal cancer
CRO	Contract Research Organisation
CRF	Case report form
CT	Computerized tomography
DRG	Diagnosis related group
ECOG	Eastern Cooperative Oncology Group
EOO	End of observation
eCRF	Electronic case report form
EGF	Epidermal growth factor
EGFR	Epidermal growth factor receptor
EDC	Electronic data capture
ELISA	Enzyme-Linked Immunosorbent Assay
ER	Emergency room
FLFAS	First Line Full Analysis Set
FOLFOX	FOL (Folinic acid, Leucovorin) F (Fluorouracil – 5FU) OX (Oxaliplatin)
FOLFIRI	FOL (Folinic acid, Leucovorin) F (Fluorouracil – 5FU) IRI (Irinotecan)
ICH GCP	International Conference on Harmonization Good Clinical Practice
ICU	Intensive Care Unit
IEC	Independent ethics committee
IFL	Irinotecan, leucovorin (folinic acid), and fluorouracil
KRAS	Kirsten rat sarcoma viral oncogene homolog
mCRC	Metastatic colorectal cancer
MRI	Magnetic resonance imaging
NCI-CTC	National Cancer Institute Common Terminology Criteria
OS	Overall survival
PFS	Progression-free survival
RECIST	Response Evaluation Criteria In Solid Tumours
SADR	Serious adverse drug reaction
SLFAS	Second Line Full Analysis Set

Abbreviation or Term	Definition/Explanation
SmPC	Summary of Product Characteristics
VEGF	Vascular Endothelial Growth Factor
Source Data	Information from an original record or certified a copy of the original record containing patient information for use in observational research. The information may include, but is not limited to observations necessary for the reconstruction and evaluation of the study. Source data are contained in source documents (original records or certified copies). Examples of source data include Subject ID.
Study day 1	Defined as the first day that Vectibix® was administered in combination with chemotherapy to the subject in routine clinical practice
End of observation (EOO) for individual subject	Defined as the last day that protocol-specified observation data is collected for an individual subject. Subjects will be followed-up until approximately 30 days after the end of Vectibix® treatment, death, withdrawal of consent, loss to follow-up, or up to 12 months from the first dose of Vectibix®, whichever occurs first. This will also mark the end of study for a subject.

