### **4.3 Internal Validity of Study Design**

#### **4.3.1 Selection Bias**

We do anticipate some degree of selection bias within our study. Since we are not recruiting patients until they have been dosed with Vectibix® at least once, there is a

small group of patients who we will not be sampling ie, those who do not commence treatment, or cease treatment very soon after the first dose, usually because of death or disease progression. Therefore the response rate may be inflated slightly and other collected data impacted. Note that in Germany we may only be able to obtain limited data from deceased patients. However generally for most patients this will not limit inclusion of patient data into the study as the study is mainly prospective in design and patients will be alive at study enrolment (where consent is required). Should subjects die during the course of the study it may become more difficult to obtain complete follow up information if the notes are then subsequently filed elsewhere and we need informed consent to obtain them.

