### 5.2.2 Analysis Subsets

First Line FOLFOX Analysis Set (FLFAS): all enrolled subjects who have received at least one infusion of Vectibix® in combination with FOLFOX as first-line treatment, a maximum of 42 days before entering study.

Second Line FOLFIRI Analysis Set (SLFAS): all enrolled subjects who have received at least one infusion of Vectibix® in combination with FOLFIRI as second-line treatment and have received first-line fluoropyrimidine-based chemotherapy (excluding irinotecan), a maximum of 42 days before entering study.

FLFAS and SLFAS are the primary analysis sets for all analyses. Selected sensitivity analyses may be performed to assess the impact of using other analysis sets.

The data will be summarized by country to fulfil local post reimbursement requirements.

---

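### The 42-day entry rule is tied to any infusion rather than the first, so as worded it also admits patients many months into treatment and biases discontinuation and exposure

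*Protocol*

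**What the plan says.** Inclusion criterion 3.5.7 covers "Subjects treated with at least one infusion of Vectibix® in combination with chemotherapy a maximum of 42 days before entering study", first line with FOLFOX or second line with FOLFIRI. The synopsis criterion reads the same. Section 3 repeats it: "Enrolled subjects must have received at least one infusion of Vectibix® in combination with chemotherapy a maximum of 42 days before entering study". Section 5.2.2 builds it into the first-line set, whose members have "received at least one infusion of Vectibix® in combination with FOLFOX as first-line treatment, a maximum of 42 days before entering study", and the second-line set is worded in parallel.

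Other time anchors in the protocol do name the first dose:

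- Criterion 3.5.6, directly above: "Tumour assessment (ie, CT/MRI) within 12 weeks (84 days) prior to first Vectibix® infusion".
- Study day 1 in the Glossary: "Defined as the first day that Vectibix® was administered in combination with chemotherapy to the subject in routine clinical practice".
- The follow-up limit in Section 3.3.2: "up to 12 months from the first dose of Vectibix®, whichever occurs first".

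Under Section 5.6.2.1, discontinuation is a number and percentage over the observation period, and exposure duration, cumulative dose and infusion count run from initiation. Section 4.3.1 names the patients the design misses: "Since we are not recruiting patients until they have been dosed with Vectibix® at least once", it loses those who never start or who stop very soon after the first dose, and it calls them few. Section 6 describes the study as largely prospective.

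**The concern.** Read literally, the rule asks only for a recent infusion. A patient nine months into treatment who was infused last week meets it. A patient who started on the same day and stopped after four months does not. Neither exclusion criterion separates the two, and the retrospective period from baseline to enrolment has no maximum length. Patients who enter late are in the study because they stayed on treatment. Abstracting their records back to baseline does not recover the patients who were never sampled.

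The affected quantities are the primary outcomes. The literal rule also conflicts with Section 4.3.1, because the missed patients would then include anyone who started before a centre opened and stopped more than 42 days before enrolment could take place. With 50 to 100 centres, one sentence can be applied in two ways, and any difference between France and Germany would carry into the country summaries.

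**Working it through.** **Yardstick from the plan.** Table 1 uses half-width = 1.96 × √(p(1−p)/n). At p = 0.5 this gives 1.96 × √(0.25/350) = 5.24% for France and 1.96 × √(0.25/390) = 4.96% for Germany, matching the printed 5.2% and 5.0%. These figures do not depend on the entry rule and serve only as a scale for the bias.

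**Inputs from the protocol.** PFS medians with panitumumab are 6.7 months (FOLFIRI, second line) and 10.0 months (FOLFOX, first line), from Section 2.2.2. Enrolment lasts E = 12 months (Section 3.3.1). The label was extended in November 2011 (Section 2.1) and Amendment 1 is dated September 2012, so a pool of P = 10 months of earlier starters is possible.

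**Assumptions.** Time on treatment is exponential with the PFS median m as a proxy, so S(t) = exp(−λt) with λ = ln 2/m. Starts occur at a constant rate. The window is g = 42/30.4375 = 1.380 months. Under a first-infusion rule, entry is uniform over 0 to g after the first dose and subjects are on treatment at entry. Under the literal rule, earlier starters are assessed when the centre opens and qualify if their last infusion was within the window, that is, if time on treatment exceeds time since first dose minus g. Later starters enter as under the first-infusion rule.

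**Formulas.**

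- Probability of still being on treatment at entry, new starters: A = (1 − S(g))/(λg).
- First-infusion rule: discontinued by t = 1 − S(t)/A.
- Weight of literal-rule subjects entering more than 42 days after first dose: L = (1 − S(P−g))/λ.
- Total literal-rule weight: W = g + L + E·A. Share entering late = L/W.
- Weight still on treatment at 6 months: R = (6+g)·S(6) + (S(6) − S(P−g))/λ + E·S(6). At 12 months: R = (P+E)·S(12). Literal rule: discontinued by t = 1 − R/W.

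**Second line, m = 6.7.** λ = 0.10345, A = 0.9319, L = 5.704, W = 1.380 + 5.704 + 11.183 = 18.27 (rounded). Late share = 5.704/18.27 = 31%. At 6 months S = 0.5376: first-infusion 1 − 0.5376/0.9319 = 42.3%; literal 1 − (5.201 + 6.451)/18.27 = 36.2%. At 12 months S = 0.2890: first-infusion 69.0%; literal 1 − 22 × 0.2890/18.27 = 65.2%.

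**First line, m = 10.0.** λ = 0.06931, A = 0.9537, L = 6.489, W = 1.380 + 6.489 + 11.444 = 19.31. Late share = 34%. At 6 months S = 0.6598: first-infusion 30.8%; literal 1 − (6.450 + 7.917)/19.31 = 25.6%. At 12 months S = 0.4353: first-infusion 54.4%; literal 1 − 22 × 0.4353/19.31 = 50.4%.

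| | All starters, 1 − S(t) | First-infusion rule | Literal rule | Literal minus first-infusion |
|---|---|---|---|---|
| Second line, 6 months | 46.2% | 42.3% | 36.2% | −6.1 |
| Second line, 12 months | 71.1% | 69.0% | 65.2% | −3.8 |
| First line, 6 months | 34.0% | 30.8% | 25.6% | −5.2 |
| First line, 12 months | 56.5% | 54.4% | 50.4% | −3.9 |

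A simulation of one million subjects agrees to about 0.1 point. It also gives median time on treatment, capped at 12 months, rising from 7.4 to 8.5 months (second line) and from 10.7 to 11.9 months (first line). Cumulative dose and infusion count move in the same direction.

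**Sensitivity.** With pools of 6 to 12 months and enrolment of 3 to 12 months, the late share runs from 23 to 64%. The shortfall against the first-infusion rule runs from about 2 to 13 points at 6 months and from about 1 to 10 points at 12 months.

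**The case against.** The strongest reply is that the protocol means new users. Section 4.3.1 makes sense only if entry closely follows the first dose, baseline history refers to the initial infusions, later doses are recorded prospectively, and the 24-month timetable fits early entry. This is persuasive as to intent, and a reader should not infer that the sponsor chose to enrol long-term users. But the operative text in the criteria, the design section and the analysis sets does not say so, although criterion 3.5.6 shows that the authors named the first infusion when they meant it.

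Three further points limit the concern:

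- Late entry is bounded in practice. Data collection stops 12 months after the first dose, so nobody beyond that can contribute prospective data.
- A reader might infer a far larger bias, for example 12-month second-line discontinuation of about 50% instead of 71%. That requires every subject to enter at a uniformly spread time over the first year and everyone who has stopped by entry to be excluded. The documents support neither. The literal rule keeps those infused within 42 days, and allowing for this alone gives about 56%.
- A reader might also object that subjects who stop within the first weeks are lost even under a first-infusion rule, or that no delayed-entry analysis is described. Section 4.3.1 discloses the first. The second may sit in an analysis plan that is not shown. Neither is part of this point.

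**Conclusion.** The point holds as a defect of wording in an eligibility rule that is repeated in both primary analysis sets. An analysis plan cannot repair it by redefining terms, because the rule decides who is sampled. Followed literally, it biases crude discontinuation downward and exposure duration, cumulative dose and infusion count upward, and it contradicts the protocol's own account of whom it misses.

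In the base illustration the shortfall in discontinuation is 5 to 6 points at 6 months and about 4 points at 12 months, relative to a first-infusion rule. That is comparable with the 5.0 to 5.2% half-width for all subjects in a country and smaller than the French half-widths at p = 0.5 for unresectable first-line (7.6%) and second-line (8.3%) subjects. Unlike sampling error, it does not shrink with more subjects.

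The size rests on an assumed pool of earlier starters, exponential times and PFS as a proxy for time on treatment. If centres enrol only new starters, the effect vanishes. No calculation was made for dose reductions or response, so no size is claimed for them.

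**What to change.** In the synopsis inclusion criteria, Section 3, criterion 3.5.7 and both analysis-set definitions in Section 5.2.2, replace the present phrase with: whose first infusion of Vectibix in combination with FOLFOX (first line) or FOLFIRI (second line) was given no more than 42 days before enrolment. All of these places must change together, or the amendment creates a new inconsistency.

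If patients already on treatment are wanted, say so explicitly, correct the description of the missed patients in Section 4.3.1 and of the prospective design in Section 6, and estimate discontinuation with delayed entry at the enrolment date.

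The first option costs a few words. Its small downside is that patients already long on treatment can no longer be enrolled.
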